**Medical Monitor Name and Contact Information will be provided separately.**

## Protocol Amendment Summary of Changes Table

DOCUMENT HISTORY	
Document	Date
Amendment a	27-Jan-2021
Original Protocol	01-Sep-2020

### Amendment b

#### Overall Rationale for the Amendment:

This amendment allows for better characterization of the incidence and severity of ARIA at an earlier time point.

Section # and Name	Description of Change	Brief Rationale
1.3. Schedule of Activities	
Added MRI at V2. Added text to Comment field about MRI at V2, including text about MRI timings relative to the first and fourth infusions.
 
Changed V2 interval tolerance from “±7” days to “-7 to +10” days.
	To allow for better characterization of the incidence and severity of ARIA at an earlier time point.
6.5.1. Standard of Care for Alzheimer’s Disease	Added “When medically indicated, initiation, increase, or discontinuation of symptomatic treatments for AD is permitted.”	Clarification.
7.1. Discontinuation of Study Intervention	Added cross-reference to the Manual of Operations regarding information about permanent discontinuation guidance.	To provide further guidance.
7.1.1.1. Due to ARIA	
Added cross-references to the Manual of Operations regarding information about temporary and permanent discontinuation guidance.
 
Modified text regarding considering reinitiating IP.
	To provide further guidance.
8.2.5. Magnetic Resonance Imaging	Added text, “Unscheduled MRIs may be performed at the discretion of investigator.”	Recommendation of DMC.

Section # and Name	Description of Change	Brief Rationale
8.3.6.2. Dosing Rechallenge and Premedication for Infusions	Added dosing rechallenge details.	Clarification/providing information.
8.3.7. Amyloid-Related Imaging Abnormalities (ARIA-E and ARIA-H)	Added text “While most cases of ARIA-E are asymptomatic, serious cases have been reported. Available data suggest serious cases are most likely to occur early in dosing, after the first, second, or third infusion. ”	Provided additional information.

## 1. Protocol Summary

### 1.1. Synopsis

**Protocol Title:** Donanemab Follow-On Study: Safety, Tolerability, And Efficacy in Symptomatic Alzheimer's Disease with Validation of Remote Neuropsychological Assessments

**Short Title:** Donanemab Follow-On Study, with Validation of Remote Scale Assessment

#### Rationale:

#### Part A

Remote assessments of individuals with AD via telemedicine have the potential to reduce burdens associated with clinical care and research participation. Research comparing clinical interviewing conducted through video conferencing and traditional on-site conditions has suggested generally good agreement in a variety of conditions, including dementia and cognitive impairment of various causes. However, limited data is available on the validity of remote web-based assessment of cognitive and functional measures typically implemented in AD research studies. Therefore, the aim of Study I5T-MC-AACH (AACH) Part A is to evaluate the validity of remote (at-home) video assessments of cognitive and functional measures.

Study AACH Part A is a multicenter, randomized, multiple crossover study to validate remote assessment of cognitive and functional scales. Participants will be assessed remotely (through videoconferencing) as well as on-site.

#### Part B

Part B is a multicenter, open-label study of donanemab treatment for participants with symptomatic AD and naïve to donanemab.

Study AACH Part B will provide additional safety and clinical information as an open-label study. Participants from a sponsor-approved originating donanemab study who were assigned placebo will receive donanemab in the single open-label arm.

#### Part C

Those who received donanemab in an originating study may participate in a single imaging and cognitive/functional assessment visit.

Study AACH Part C will assess the long-term effect of donanemab on PET imaging biomarkers, cognition, and functioning in participants who have not received IP for at least 52 weeks.

**Objectives and Endpoints**

Objectives	Endpoints
Primary	
Part A To evaluate the reliability of VTC compared with on-site administered cognitive and functional measures	The intraclass correlation between VTC and on-site assessment for PAIR 1 for 
 
• ADAS-Cog13
 
• ADCS-ADL
 
• MMSE
 
• CDR-SB
 

Part B To evaluate safety and tolerability of donanemab	Standard safety assessments in Part B: 
 
• Spontaneously reported AEs
 
• Clinical laboratory tests
 
• Vital sign and body weight measurements
 
• 12-lead ECGs
 
• Physical and neurological examinations
 
 MRI (ARIA and emergent radiological findings) Infusion-related reactions C-SSRS
Secondary	
To assess the effect of donanemab on clinical progression in participants with symptomatic AD	Change from baseline up to Week 72 as measured in Part B by: 
 
• MMSE score
 
• ADAS-Cog13 score
 
• iADRS score
 
• ADCS-iADL score
 
• CDR-SB
 

To assess the effect of donanemab on brain amyloid deposition	Change in brain amyloid plaque deposition from baseline at Week 36 of Part B as measured by florbetapir F 18 PET scan

To assess the effect of donanemab on brain region volumes	Change in volumetric MRI measures from baseline to Week 72 in Part B
To assess peripheral PK and presence of anti-donanemab antibodies	
PK of donanemab in Part B.
 
ADAs against donanemab in Part B including
 
 
• treatment-emergent ADAs
 
• neutralizing antibodies
 

Abbreviations: AD = Alzheimer's disease; ADA = antidrug antibody; ADAS-Cog13 = Alzheimer's Disease Assessment Scale – Cognitive subscale; ADCS-ADL = Alzheimer's Disease Cooperative Study – Activities of Daily Living Inventory; ADCS-iADL = Alzheimer's Disease Cooperative Study – instrumental Activities of Daily Living; AE = adverse event; ARIA = amyloid-related imaging abnormality; CDR-SB = Clinical Dementia Rating Scale – Sum of Boxes; C-SSRS = Columbia Suicide Severity Rating Scale; ECG = electrocardiogram; iADRS = integrated Alzheimer's Disease Rating Scale; MMSE = Mini Mental State Examination; MRI = magnetic resonance imaging; PET = positron emission tomography; PK = pharmacokinetics; VTC = video teleconference.

## Overall Design

### Part A:

The video validation period is a multiple crossover design with participants alternating between in-clinic assessments and at-home assessments of cognitive and functional scales over a minimum of 1 and a maximum of 3 crossovers. Total time in Part A can vary from a minimum of 4 weeks (1 crossover [1 PAIR]) to a maximum of 24 weeks (3 crossovers [3 PAIRS]). Participants do not receive study IP during the video validation period. Participants are randomized 1:1 in regards to order of in-clinic or at-home for the first assessment, either:

- Group 1: Cognitive/functional scale assessment at the study site (on-site), followed by an at-home assessment (VTC), or
- Group 2: Cognitive/functional scale assessment at home (VTC), followed by assessment on-site.

### Part B:

Part B is a multicenter, open-label, follow-on study of donanemab in participants with symptomatic AD. Participants who received placebo in the originating trial receive donanemab 700 mg IV Q4W for 3 doses, then 1400 mg intravenously every 4 weeks for up to 36 weeks, (up to 48 weeks total duration in Part B).

Participants may receive donanemab through Week 36 or Week 48. Criteria for scheduled dose discontinuation at 36 weeks are defined by the sponsor and may be based on results of the participant's florbetapir F 18 PET scan at Week 36 or results from external studies such as Study AACG.

### Part C:

Participants who received donanemab in the originating trial may participate in an imaging and cognitive/functional assessment visit (Visit 201). Visit 201 occurs anytime at least 52 weeks from the participant's last double-blind visit in the originating study.

**Disclosure Statement:**

This is a single-arm treatment study with 1 arm that is not blinded.

**Number of Participants:**

Approximately 200 participants will be enrolled such that approximately 150 participants complete the study.

**Intervention Groups and Duration:**

Part A: The video validation period is a multiple crossover design with participants alternating between in-clinic assessment and at-home assessment of cognitive and functional scales over a minimum of 1 and a maximum of 3 crossovers. Total time in Part A can vary from a minimum of 4 weeks (1 crossover [1 PAIR]) to a maximum of 24 weeks (3 crossovers [3 PAIRS]).

Participants do not receive study IP during the video validation period. Participants are randomized 1:1 in regards to order of in-clinic or at-home for the first assessment, either:

- Group 1: Cognitive/functional scale assessment at the study site (on-site), followed by an at-home assessment (VTC; video teleconference) or
- Group 2: Cognitive/functional scale assessment at home (VTC), followed by assessment on-site.

Part B: Participants who received placebo in the originating trial receive donanemab 700 mg IV Q4W for 3 doses, then 1400 mg IV every 4 weeks for up to 36 weeks (up to 48 weeks total duration in Part B).

Part C: Participants who received donanemab in the originating trial may participate in an imaging and cognitive/functional assessment visit (Visit 201). Visit 201 occurs anytime at least 52 weeks from the participant's last double-blind visit in the originating study.

[figure not shown]
The maximum total duration of study participation for each participant, including screening and the posttreatment follow-up periods, is up to 124 weeks:

- Screening: up to 30 days prior to Visit 602
- Part A, Video assessment: up to 24 weeks
- Part B, Open-label donanemab: up to 72 weeks (treatment received for 36 or 48 weeks)
- Part B, Follow-up: up to 24 weeks

Note: Part C is not added to the maximum total duration of study participation because Part C is a single visit, and Part B participants do not participate in Part C.

**Data Monitoring Committee: No**

## 1.2. Schema

Abbreviations: IP = investigational product; IV = intravenous; LY = donanemab; PBO = placebo; Q4W = every 4 weeks; SoA = Schedule of Activities; V = visit.

- \* Participant should participate in PAIR 1 to proceed to Part B or Part C. V601 occurs up to 30 days prior to V602. Visits in Part A are each separated by 4 weeks. The time between the final visit of Part A and the first visit of Part B or Part C is  $\geq 4$  weeks.
- ◆ IP is administered up to V13 but may be discontinued as early as V10. Visits continue until end of study as indicated in the SoA.
- Imaging and cognitive & functional measures visit occurs any time  $\geq 52$  weeks after the participant's last double-blind visit in the originating study. See V201 in the SoA for procedures.

### 1.3. Schedule of Activities (SoA)

#### Screening and Part A

	Screening	Part A: Video Validation		Comments
Visit Number	601	602-607		
Weeks Relative to Baseline (V1)	See footnote a.			
Visit Interval Tolerance (days)	—	±4	±4	
Entry and Administrative				
Full informed consent (participant and study partner)	X			
Inclusion and exclusion criteria, review and confirm	X			
Interval medical history, including relevant changes since last visit of originating study	X			
Substance use (alcohol, caffeine, tobacco use)	X			
Concomitant medications	X	X	X	
AEs	X	X	X	
Clinical Assessments				
Physical/neurological examination	X			Complete physical and neurological exam, as described in Section 8.2.1. Any clinically significant changes from baseline on physical/neurological examinations should be noted on the AE CRF.

	Screening	Part A: Video Validation		Comments
Visit Number	601	602-607		
Weeks Relative to Baseline (V1)	See footnote a.			
Visit Interval Tolerance (days)	—	±4	±4	
Clinician-Administered Assessments (Electronic)				
ADAS-Cog 13		X	X	Administer the ADAS-Cog 13 , ADCS-ADL, CDR-SB, and MMSE prior to medical procedures that could be stressful to the participant (blood draws, etc.; Section 8.1.2). These tests include the audio voice recording of the rater's questions and the participant and study partner responses to assessment questions.
ADCS-ADL		X	X	
CDR-SB		X	X	
MMSE		X	X	
Randomization				
Randomization	X			

## Part B

		Part B: Open-Label															Part B: Follow-Up, UV, ED				Comments
		1	2	3	4	5	6	7	8	9	10	11 c	12 c	13 c	14 c	15	801 d	802 d	UV	ED	
Visit Number	UP b	1	2	3	4	5	6	7	8	9	10	11 c	12 c	13 c	14 c	15	801 d	802 d	UV	ED	ED only if participant has completed V1 and received IP in Part B.
Weeks Relative to Baseline (V1)		0	4	8	12	16	20	24	28	32	36	40	44	48	60	72	84	96	997		Procedures for some visits may take more than 1 day.
Visit Interval Tolerance (days)		—	-7 to +10	±7	±7	±7	±7	±7	±7	±7	±7	±7	±7	±7	±7	±7	±7	±7			
Entry and Administrative																					
Review MRI, clinical labs, and clinical status		X																			Confirm participant does not meet discontinuation criteria (Section 7.2).
Concomitant medications		X	X	X	X	X	X	X	X	X	X	X	X	X	X	X	X	X	X		
AEs		X	X	X	X	X	X	X	X	X	X	X	X	X	X	X	X	X	X		
Clinical Assessments																					
Height		X																			
Weight		X			X			X			X			X	X			X	X	X	

		Part B: Open-Label																	Part B: Follow-Up, UV, ED				Comments	
		Visit Number	UP b	1	2	3	4	5	6	7	8	9	10	11 c	12 c	13 c	14 c	15	801 d	802 d	UV	ED		
Weeks Relative to Baseline (V1)		0		4	8	12	16	20	24	28	32	36	40	44	48	60	72	84	96	997				Procedures for some visits may take more than 1 day.
Visit Interval Tolerance (days)		-	-7 to +10	±7	±7	±7	±7	±7	±7	±7	±7	±7	±7	±7	±7	±7	±7	±7	±7	±7				
Vital signs			X	X	X	X	X	X	X	X	X	X	X	X	X	X	X	X	X	X	X			Sitting BP, pulse, and temperature (with sitting vitals) will be measured at all visits. Sitting BP and pulse will be measured after approximately 5 minutes in the sitting position only. In addition, orthostatic BP and pulse will be measured at V1, V4, V7, V10, V13, V14, ED, and UVs.
Physical/neurological examination			X			X		X			X		X		X		X		X	X	X			Includes neurological examination V601 is a brief physical and neurological exam, as described in Section 8.2.1. Any clinically significant changes from baseline on physical/neurological examinations should be noted on the AE CRF.

		Part B: Open-Label															Part B: Follow-Up, UV, ED			Comments	
		1	2	3	4	5	6	7	8	9	10	11 c	12 c	13 c	14 c	15	801 d	802 d	UV	ED	
Visit Number	UP b	1	2	3	4	5	6	7	8	9	10	11 c	12 c	13 c	14 c	15	801 d	802 d	UV	ED	ED only if participant has completed V1 and received IP in Part B.
Weeks Relative to Baseline (V1)		0	4	8	12	16	20	24	28	32	36	40	44	48	60	72	84	96	997		Procedures for some visits may take more than 1 day.
Visit Interval Tolerance (days)		—	-7 to +10	±7	±7	±7	±7	±7	±7	±7	±7	±7	±7	±7	±7	±7	±7	±7			
12-lead ECG (central or local)		X			X			X			X			X	X				X		Perform prior to administration of IP, when appropriate. ECG at V14 not required for participants who completed dosing at V10.

		Part B: Open-Label															Part B: Follow-Up, UV, ED				Comments		
		Visit Number	UP b	1	2	3	4	5	6	7	8	9	10	11 c	12 c	13 c	14 c	15	801 d	802 d	UV	ED	
Weeks Relative to Baseline (V1)		0		4	8	12	16	20	24	28	32	36	40	44	48	60	72	84	96	997			Procedures for some visits may take more than 1 day.
Visit Interval Tolerance (days)		—		-7 to +10	±7	±7	±7	±7	±7	±7	±7	±7	±7	±7	±7	±7	±7	±7	±7	±7			
PET Scans and MRI																							Perform prior to V1 at UP if last recorded MRI from originating study occurred >12 months before V1.
MRI			X		X		X					X					X				X		MRI at V2 is to be performed and reviewed prior to V2 infusion and may occur no sooner than 21 days after the first infusion. If infusions are suspended after the first, second, or third dose, an MRI is to be performed and reviewed prior to the fourth infusion.  MRI at V4 is to be performed and reviewed prior to V4 infusion.  MRI at V4 may occur 14 days before the scheduled visit date without protocol deviation.

		Part B: Open-Label															Part B: Follow-Up, UV, ED				Comments			
		Visit Number	UP b	1	2	3	4	5	6	7	8	9	10	11 c	12 c	13 c	14 c	15	801 d	802 d	UV	ED		
Weeks Relative to Baseline (V1)		0		4	8	12	16	20	24	28	32	36	40	44	48	60	72	84	96	997			Procedures for some visits may take more than 1 day.	
Visit Interval Tolerance (days)		-		-7 to +10	±7	±7	±7	±7	±7	±7	±7	±7	±7	±7	±7	±7	±7	±7	±7	±7				
Florbetapir F 18 PET scan													X									X e	Florbetapir F 18 PET scan may occur ±14 days from scheduled visit date without protocol deviation.	
Clinician-Administered Assessments (Electronic)																								
ADAS-Cog 13			X			X			X			X			X	X	X	X	X		X		Administer the ADAS-Cog 13 , ADCS-ADL, CDR-SB, and MMSE prior to medical procedures that could be stressful to the participant (blood draws, etc.; Section 8.1.2). These tests include the audio voice recording of the rater's questions and the participant and study partner responses to assessment questions.	
ADCS-ADL			X			X			X			X			X	X	X	X	X		X			
CDR-SB (Global Sum of Boxes - CDR)			X			X			X			X			X	X	X	X	X		X			
MMSE			X			X			X			X			X	X	X	X	X		X			
Clinician-Administered Assessments (Paper)																								
C-SSRS Screening/Baseline			X																					

		Part B: Open-Label																	Part B: Follow-Up, UV, ED				Comments	
		1	2	3	4	5	6	7	8	9	10	11 c	12 c	13 c	14 c	15	801 d	802 d	UV	ED				
Visit Number	UP b	1	2	3	4	5	6	7	8	9	10	11 c	12 c	13 c	14 c	15	801 d	802 d	UV	ED	ED only if participant has completed V1 and received IP in Part B.			
Weeks Relative to Baseline (V1)		0	4	8	12	16	20	24	28	32	36	40	44	48	60	72	84	96	997			Procedures for some visits may take more than 1 day.		
Visit Interval Tolerance (days)		—	-7 to +10	±7	±7	±7	±7	±7	±7	±7	±7	±7	±7	±7	±7	±7	±7	±7	±7					
C-SSRS Since Last Visit			X	X	X	X	X	X	X	X	X	X	X	X	X	X	X	X	X	X	X			
Self-Harm Supplement Form			X	X	X	X	X	X	X	X	X	X	X	X	X	X	X	X	X	X	X			
Self-Harm Follow-Up Form			X	X	X	X	X	X	X	X	X	X	X	X	X	X	X	X	X	X	X	Required if triggered by the Self-Harm Supplement Form per instructions.		
Laboratory Tests and Sample Collectionsf																								
Hematology		X	X	X	X	X			X			X			X	X						X	Labs at V14 not required for participants who completed dosing at V10. Perform prior to V1 at UP if last recorded labs from the originating study were collected >6 months before V1.	
Clinical Chemistry		X	X	X	X	X			X			X			X	X						X		
P-tau			X			X			X			X			X	X	X	X	X		X			
NfL			X			X			X			X			X	X	X	X	X		X			
Aβ			X			X			X			X			X	X	X	X	X		X			

		Part B: Open-Label																Part B: Follow-Up, UV, ED				Comments	
		Visit Number	UP b	1	2	3	4	5	6	7	8	9	10	11 c	12 c	13 c	14 c	15	801 d	802 d	UV	ED	
Weeks Relative to Baseline (V1)		0		4	8	12	16	20	24	28	32	36	40	44	48	60	72	84	96	997			Procedures for some visits may take more than 1 day.
Visit Interval Tolerance (days)		-		-7 to +10	±7	±7	±7	±7	±7	±7	±7	±7	±7	±7	±7	±7	±7	±7	±7	±7			
PK sample (predose)				X	X		X		X			X			X								Do not collect if the last IP infusion was >6 months prior to the scheduled visit. Predose collections may be collected from the IV site prior to the infusion.  Random PK sample collected for participants who do not receive dose at V13.
PK sample (postdose)			X			X		X															Do not collect if the last IP infusion was >6 months prior to the scheduled visit. Collect within 30 minutes of IP administration. Collect from the arm that IP was not administered through.
PK sample (random)																X	X	X	X		X		Do not collect if the last IP infusion was >6 months prior to the scheduled visit.
Immunogenicity (ADA) samples			X	X	X		X		X			X			X	X	X	X	X		X		

		Part B: Open-Label																	Part B: Follow-Up, UV, ED				Comments	
		1	2	3	4	5	6	7	8	9	10	11 c	12 c	13 c	14 c	15	801 d	802 d	UV	ED				
Visit Number	UP b	1	2	3	4	5	6	7	8	9	10	11 c	12 c	13 c	14 c	15	801 d	802 d	UV	ED	ED only if participant has completed V1 and received IP in Part B.			
Weeks Relative to Baseline (V1)		0	4	8	12	16	20	24	28	32	36	40	44	48	60	72	84	96	997		Procedures for some visits may take more than 1 day.			
Visit Interval Tolerance (days)		—	-7 to +10	±7	±7	±7	±7	±7	±7	±7	±7	±7	±7	±7	±7	±7	±7	±7	±7					
Stored Samples																								
Exploratory biomarker samples			X			X			X			X				X			X		X		X	Collect unless not allowed or unfeasible due to local regulations.
Randomization and Dosing																								
Contact IWRS - dispensation of IP		X	X	X	X	X	X	X	X	X	X	X	X	X										Only contact IWRS at V11, V12, and V13 for participants receiving IP for 48 weeks.
Administer IP		X	X	X	X	X	X	X	X	X	X	X	X	X										Administered by IV at study site. The participant should be observed for a minimum of 60 minutes following the end of each infusion. Only administer IP at V11, V12, and V13 for participants receiving IP for 48 weeks.

## Part C

	Part C	Comments
Visit Number	201	
Timing	Any time $\geq$ 52 weeks after participant's last double-blind visit in the originating study.	Procedures may take more than 1 day.
PET Scans		
Flortaucipir F 18 PET scan	X g	
Florbetapir F 18 PET scan	X g	
Clinician Administered Assessments (Electronic)		
ADAS-Cog 13	X	If a PET scan is done on the same day, administer the ADAS-Cog 13 , ADCS-ADL, CDR-SB, and MMSE prior to PET scan. These tests include the audio voice recording of the rater's questions and the participant and study partner responses to assessment questions.
ADCS-ADL	X	
CDR-SB (Global Sum of Boxes - CDR)	X	
MMSE	X	
P-tau	X	
NfL	X	
A $\beta$	X	
Exploratory biomarker samples	X	Collect unless not allowed or unfeasible due to local regulations.
AEs	X	
Concomitant medications	X	

Abbreviations: A $\beta$  = amyloid beta; ADA = antidrug antibody; ADAS-Cog13 = Alzheimer's Disease Assessment Scale – Cognitive subscale; ADCS-ADL = Alzheimer's Disease Cooperative Study – Activities of Daily Living Inventory; AE = adverse event; BP = blood pressure; CDR-SB = Clinical Dementia Rating Scale – Sum of Boxes; C-SSRS = Columbia Suicide Severity Rating Scale; CRF = case report form; ECG = electrocardiogram; ED = early discontinuation; IP = investigational product; IV = intravenous; IWRS = interactive web-response system; MMSE = Mini Mental State Examination; MRI = magnetic resonance imaging; NfL = neurofilament light chain; PET = positron emission tomography; PK = pharmacokinetics; P-tau = phosphorylated tau; UP = unscheduled procedure; UV = unscheduled visit; V = visit.

- a V601 occurs up to 30 days prior to V602. V602 cannot occur <30 days from the participant's last double-blind visit of the originating study. V602 through V607 each occur 4 weeks apart. Part A visits may occur up to 24 weeks prior to Part B (V1), for eligible participants. The exact week relative to V1 depends on the number of PAIRs in which the participant elects to participate. The time between the final visit of Part A and the first visit of Part B or Part C is  $\geq$ 4 weeks.
- b UP takes place at the start of Part B (prior to V1), and is only conducted if: participant's last MRI from the originating study is >12 months from V1, or last labs from the originating study were collected >6 months from V1. The investigator confirms continued eligibility as described in Section [7.2](#).
- c V11 and V12 do not occur for participants with a final dose at or before V10. Participants resume the visit schedule with V13 (Week 48). V14 may be optional for some participants, as determined by the sponsor.
- d Follow-up visits are not required if the participant meets release requirements determined by the sponsor.
- e For Part B ED visit, collect florbetapir F 18 PET scan only if a florbetapir F 18 PET scan has not yet been performed and participant has received at least 3 doses of donanemab.
- f Unscheduled lab tests may be performed at the discretion of the investigator. Collect labs prior to administration of IP, unless otherwise noted.
- g Perform the flortaucipir F 18 and florbetapir F 18 PET scans  $\geq$ 16 hours apart from each other.

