### 3. Objectives and Endpoints

Objectives	Endpoints
Primary	
Part A To evaluate the reliability of VTC compared with on-site administered cognitive and functional measures	The intraclass correlation between VTC and on-site assessment for PAIR 1 for 
 
• ADAS-Cog13
 
• ADCS-ADL
 
• MMSE
 
• CDR-SB
 

Part B To evaluate safety and tolerability of donanemab	Standard safety assessments in Part B: 
 
• Spontaneously reported AEs
 
• Clinical laboratory tests
 
• Vital sign and body weight measurements
 
• 12-lead ECGs
 
• Physical and neurological examinations
 
 MRI (ARIA and emergent radiological findings) Infusion-related reactions C-SSRS
Secondary	
To assess the effect of donanemab on clinical progression in participants with symptomatic AD	Change from baseline up to Week 72 as measured in Part B by: 
 
• MMSE score
 
• ADAS-Cog13 score
 
• iADRS score
 
• ADCS-iADL score
 
• CDR-SB
 

To assess the effect of donanemab on brain amyloid deposition	Change in brain amyloid plaque deposition from baseline at Week 36 of Part B as measured by florbetapir F 18 PET scan
To assess the effect of donanemab on brain region volumes	Change in volumetric MRI measures from baseline to Week 72 in Part B
To assess peripheral PK and presence of anti-donanemab antibodies	PK of donanemab in Part B. ADAs against donanemab in Part B including 
 
• treatment-emergent ADAs
 
• neutralizing antibodies
 

Tertiary/Exploratory	

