### 6.1. Study Intervention(s) Administered

The IP used in this study is:

- Donanemab

IP is administered only during the open-label donanemab period (Part B). Participants do not receive IP during Part A or Part C.

The following clinical and imaging assessments are to be performed prior to administration of IP at Part B Visit 1:

- Visit 1 physical and neurological examination, vital signs, and ECG
- If >6 months between the final clinical laboratory assessment from the originating study and Visit 1, clinical laboratory assessment (See SoA; Section 1.3)
- If >12 months between the final centrally read MRI from the originating study and Visit 1, MRI assessment (See SoA; Section 1.3)

See Section 7 for details regarding discontinuation criteria.

IP is administered by IV infusion over a minimum of 30 minutes. Detailed instructions for administration, including infusion rate, can be found in the pharmacy manual.

Note that at visits which require cognitive assessments to be performed, all cognitive scales are to be administered before IP is administered.

IP is to be administered once Q4W. IP must not be administered at a dosing interval of <21 days at any time in the study. Based on permitted visit windows, it would appear that study medication could theoretically be administered at a 2-week interval. However, administration of 2 doses within <21 days of each other will be a protocol deviation.

See Section 6.5.2 for infusion-related reactions and premedication instructions, if applicable.

Sites must have resuscitation equipment available.

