### 9.4.3. Secondary Endpoint(s)

To assess the effect of donanemab on clinical progression in participants with symptomatic AD, MMRMs will be fit to the Part B data up to Week 72 for ADAS-Cog13, ADCS-ADL, iADRS, MMSE, and CDR-SB. The models will include terms for visit, age, years of education, and presence/absence of anti-dementia drugs. Visit will be considered a categorical variable.

Observed case analyses will also be conducted for each scale. Additionally, if participant numbers are adequate, AD progression from these models can be compared to anticipated progression had the patient remained untreated. Details of such a comparison are contained in the SAP.

Change from baseline in brain amyloid deposition at Week 36 and Week 72 of Part B will be assessed using an MMRM. The model will include terms for visit, age, years of education, and presence/absence of anti-dementia drugs. Visit will be considered a categorical variable. An observed case analysis will also be conducted.

Change from baseline in brain region volumes at Week 72 for Part B will be assessed using an ANCOVA model. The model will include terms for age, years of education, and presence/absence of anti-dementia drugs. An observed case analysis will also be conducted. The brain regions of interest will be defined in the SAP.

PK analyses will be defined by the PK scientist and will be specified in the PK analysis plan.

Categorical displays of ADAs against donanemab and neutralizing antibodies will be presented.

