7.1. General Considerations

All analyses will be limited to participants who received study drug and provided clinical, imaging, and/or biomarker data from Part B of AACH.

Baseline definitions are dependent on the quantity being assessed. For safety analyses, baseline will be defined as the last assessment collected prior to the first dose of donanemab, generally Visit 1 from Part B. For treatment-emergent safety analyses, only participants who have both a baseline observation and a postbaseline observation will be included in the analysis for each analyte or parameter, respectively. Where further clarification on baseline definitions is needed, the relevant subsections will specify the definitions.

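### Part B schedules a pre-dose MRI only when the last one is over 12 months old, and no volumetric baseline is defined, so change to Week 72 can include roughly 12 to 52 untreated weeks

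*Protocol*

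**What the plan says.** Three places in the protocol agree on when an MRI is done before the first Part B dose. Footnote b of the Schedule of Activities (Section 1.3) says the unscheduled procedure before Visit 1 (UP) takes place only if the participant's "last MRI from the originating study is >12 months from V1", or if the laboratory results are out of date. The MRI comment in the Part B schedule says "Perform prior to V1 at UP if last recorded MRI from originating study occurred >12 months before V1". Section 6.1 says "If >12 months between the final centrally read MRI from the originating study and Visit 1, MRI assessment". Visit 1 otherwise calls only for review of an existing MRI. The first MRI scheduled for every Part B participant is at Visit 2, and it "may occur no sooner than 21 days after the first infusion".

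The secondary endpoint in Section 3 is "Change in volumetric MRI measures from baseline to Week 72 in Part B". Section 9.4.3 says "Change from baseline in brain region volumes at Week 72 for Part B will be assessed using an ANCOVA model", with terms for age, years of education and anti-dementia drugs. Neither baseline volume nor scan interval is listed.

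Protocol Section 9.4.1 leaves baseline definitions to the SAP. SAP Section 7.1 gives a rule for safety analyses: "baseline will be defined as the last assessment collected prior to the first dose of donanemab, generally Visit 1 from Part B". SAP Section 7 contains no volumetric MRI analysis and no volumetric baseline. SAP Section 7.6.7 plans a table of ARIA-H shifts from baseline by visit, based on safety MRI.

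**The concern.** Part B has one arm and no placebo group, so within-person change is the whole volumetric estimate and nothing subtracts the natural course. If the baseline scan precedes the first infusion by months, the reported change mixes untreated volume loss with change on drug, in proportions that differ between participants.

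The rescan rule makes this uneven. A participant whose last MRI is just under 12 months old at Visit 1 keeps that scan, while one just over 12 months gets a new one. Two otherwise similar people could have measured intervals differing by nearly a year, and the model would treat both as a 72-week change.

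The primary safety objective is touched as well. The ARIA-H shift tables compare Visit 2 and later scans with the last pre-dose scan. A microhemorrhage that arose between that scan and the first infusion would first be seen after dosing and be counted as a post-baseline shift. Amendment b added the Visit 2 MRI in order to characterize early ARIA, so this comparison matters.

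**Working it through.** **Timeline check.** The protocol states a maximum participation of 124 weeks (Section 4.1). Its components are 30 days of screening, 24 weeks of Part A, 72 weeks of Part B and 24 weeks of follow-up: 30/7 + 24 + 72 + 24 = 124.3 weeks, which agrees. (The 124-week MRI span below is a different quantity that happens to be similar.)

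**Inputs**, all from Protocol Section 1.3, footnotes a and b, unless noted:
- last double-blind visit to V602: at least 30 days
- Part A visits: 28 days apart, tolerance ±4 days (Part A schedule)
- last Part A visit to V1: at least 28 days
- minimum Part A participation: Pair 1, that is two visits (Section 4.1.3)
- rescan before V1: only if the last MRI is more than 12 months old, about 365/7 = 52.1 weeks

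**Shortest gap from last double-blind visit to V1**, for p pairs: 30 + 28 × (2p − 1) + 28 days.
- p = 1: 30 + 28 + 28 = 86 days = 12.3 weeks (82 days = 11.7 weeks using the −4 day tolerance)
- p = 2: 30 + 84 + 28 = 142 days = 20.3 weeks
- p = 3: 30 + 140 + 28 = 198 days = 28.3 weeks

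If the last originating-study MRI was at or before the last double-blind visit, these are also the shortest gaps g from that scan to V1. The longest gap without a rescan is about 52 weeks.

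**Span of the nominal 72-week change**, with span = g + 72, untreated share = g/(g + 72) and ratio = (g + 72)/72:

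| Gap g (weeks) | Span (weeks) | Untreated share | Ratio to 72 weeks |
|---|---|---|---|
| 12.3 | 84.3 | 15% | 1.17 |
| 20.3 | 92.3 | 22% | 1.28 |
| 28.3 | 100.3 | 28% | 1.39 |
| 52.1 | 124.1 | 42% | 1.72 |

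At the 82-day minimum the share is 11.7/83.7 = 14%. For a participant rescanned at UP, g is small and the span is much closer to 72 weeks. The documents do not say how many participants fall in each group.

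The last column is a ratio of observation times. It is also the ratio of volume changes only if loss is linear in time and unaffected by drug. The documents give no atrophy rate, so the bias in volume units cannot be computed.

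**The case against.** The best reply is that no text makes an originating-study scan the volumetric baseline. The SAP 7.1 rule is worded for safety analyses, and Protocol Section 8.1.3 lists volumetric MRI among the biomarker efficacy measures. That is correct. A reader might infer that the plan fixes an old scan as baseline for everyone. It does not: the baseline is undefined, and participants past 12 months are rescanned. The last pre-dose scan is only the natural reading.

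The 12-week floor is also conditional. Sections 6.1 and 7.2 speak of the final centrally read MRI, without tying it to the last double-blind visit. Pair 1 is expected rather than strictly required (Section 4.1.3), and Section 8.2.5 allows unscheduled MRIs at the investigator's discretion. A later scan would shorten the gap. The number of pairs sets only a minimum, since footnote a puts no upper limit on the gaps before V602 or after Part A.

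It can also be said that the SAP 7.1 rule works for MRI, because the operative part is the last assessment before dosing and the reference to Visit 1 allows exceptions. That is fair; a clarification is enough there.

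Finally, Part B tests no hypothesis, and without a control even a scan at Visit 1 would not isolate a drug effect on volume. This limits the consequence but does not remove it. A change labelled as 72 weeks should cover about 72 weeks, or the report should state the interval it covers.

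**Conclusion.** The concern holds in conditional form. No pre-dose MRI is scheduled unless the last is more than 12 months old, and the volumetric baseline is undefined. If the last pre-dose scan is used, participants not rescanned have a baseline about 12 to 52 weeks before the first dose, and their change to Week 72 spans about 84 to 124 weeks, some 14% to 42% of it untreated. This rests on three assumptions: the last originating-study MRI was no later than the last double-blind visit, Pair 1 was completed, and no discretionary MRI followed. The Section 9.4.3 model ignores the difference between these participants and those rescanned.

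It would be tempting to say that volume loss is overstated by 17% to 72%. The documents do not support that, because the figure needs linear loss unaffected by drug. Likewise, the ARIA-H misattribution follows from the SAP's baseline rule, but nothing in the documents tells how often it would occur.

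The point should be acted on: following the plan can put untreated time into a secondary endpoint and pre-dose microhemorrhages into a safety table, and the remedy is an analysis change.

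**What to change.** No scan needs to be added.

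1. In Protocol Section 9.4.3, and in a Part B volumetric section to be added to the SAP, define the baseline as the last scan before the first infusion. Use actual scan dates, and include the interval from baseline scan to first infusion in the model. Annualizing the change is an alternative that the SAP already uses for Part C (Sections 8.6 to 8.8). The new section should also name the brain regions, which Section 9.4.3 leaves to the SAP.
2. As a sensitivity analysis, report change from the first post-dose scan to Week 72: Visit 2 where that scan exists and was processed for volumes, otherwise Visit 4. Participants who passed Visit 2 before Amendment b may have no Visit 2 scan, and the documents do not say whether Visit 2 scans are processed for volumes.
3. Tabulate weeks from baseline MRI to first infusion, as SAP Section 8.5 does for Part C, and show ARIA-H first seen at Visit 2 (or Visit 4 if there is no Visit 2 scan) by that interval. Clarify in SAP Section 7.1 that the MRI baseline is generally not a Visit 1 scan.

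The cost is analysis wording and a few tables. There are two limits. Interval adjustment needs an assumption about the shape of volume change. The Visit 2 or Visit 4 reference leaves out the first 4 to 12 weeks on drug, so it supplements the pre-dose baseline and does not replace it. A full repeated-measures model is optional: with one pre-dose scan and a first post-dose scan at about Week 4, it could not cleanly separate pre-dose change from early on-drug change.
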